#### PRO endpoints:

- *Acne scar appearance* using the SCARS questionnaire at baseline, week 12, week 24, week 48, early termination, for each half-face
- Subject satisfaction questionnaire at week 24, week 48, early termination

#### 9.1.2 Populations analyzed, evaluability and limitations / evaluation of bias

The statistical analyses will be performed based on the following subject populations. The definition of the populations will be finalized after a blind data review meeting.

#### 9.1.2.1 The Per Protocol efficacy population (PP)

This population will consist of all enrolled and randomized subjects, except subjects who have major deviations from the protocol. Major deviations will be defined during a data review meeting after data entry and before unblinding the clinical trial treatment. Major protocol deviations will be considered as having a possible effect on the interpretation of primary efficacy results and may include: inclusion criteria not respected, non-available efficacy assessment, interfering therapy at inclusion, etc.

The primary efficacy endpoint will be analyzed based on this population.

#### 9.1.2.2 The Intent-to-Treat efficacy population (ITT)

This population will consist of the entire population enrolled and randomized (i.e., assigned a kit number). The ITT population will be used for all variables except the safety variables.

#### 9.1.2.3 The Safety population (All patients treated [APT])

This population will consist of the Intent-to-Treat population, after exclusion of subjects who never used the treatment with certainty based on monitoring report. The APT population will be only used for the safety variables.

GALDERMA RESEARCH & DEVELOPMENT Protocol N° RD.03.SPR.105061 Page 74 of 99 CONFIDENTIAL

#### 9.1.2.4 Missing values

The last observation carried forward (LOCF) method will be used to impute missing values of acne scar and lesion counts and global assessment scores (SGA and IGA) during part I. If no post-baseline data are available, baseline will be carried forward. The other missing values of part I and the data collected during part II will not be replaced (observed data).

#### 9.1.3 Data presentation and graphics

All continuous data will be summarized using usual statistics: number of values, mean, median, standard deviation, minimum and maximum, and by frequency distribution (n, %) for qualitative data. For ordinal data, both frequency distribution and usual statistics will be presented. Tables will be presented by investigational product, bilateral difference and visit (when applicable).

Therapies that have been stopped before the baseline visit will be presented as prior therapies. Those reported at baseline and still continuing after baseline will be classified as concomitant therapies.

The adverse events will be descriptively summarized (n, %) for the safety population (APT). The adverse events will be descriptively summarized (n, %) by relationship to the investigational products within System Organ Class (SOC) and preferred term (MedDRA). Subjects will be descriptively summarized (n, %) by intensity (*i.e.* mild, moderate and severe) of adverse events, SOC and preferred terms. Deaths and serious adverse events will be reported as well as withdrawals due to adverse events. A subject will be counted only once per System Organ Class (SOC) and only once per preferred term even if more than one occurrence of an event was reported within a SOC or preferred term. In the summary by categories of intensity, the adverse event with the highest intensity will be used. The subject will be counted only once per SOC (highest intensity whatever the AE within the SOC) and once per preferred term (highest intensity whatever the AE within the preferred term).

#### 9.1.4 Statistical analyses

The primary objective of this trial is to demonstrate the superiority of Adapalene 0.3% - BPO 2.5% gel compared to its vehicle, in terms of total atrophic acne scar count at week 24. The mean bilateral difference between products of primary efficacy endpoint will be analyzed by using the Wilcoxon Rank Signed test, testing the hypothesis of equality. The p-value will have to be inferior to 0.05 at week 24, on ITT/LOCF population. Per Protocol analysis will be also performed to assess the robustness of the results obtained on the ITT/LOCF population.

GALDERMA RESEARCH & DEVELOPMENT Protocol N° RD.03.SPR.105061 Page 75 of 99 CONFIDENTIAL

The other efficacy variables of part I will be analyzed similarly as the primary analysis on the appropriate population. Each test will be two-sided, at the 0.050 significance level.

The subject characteristics (previous medication, concomitant medication, demographics, baseline characteristics...), lesion counts, microrelief, adverse events, local tolerability and questionnaires and all variables of part II will be summarized by descriptive statistics (usual statistics and frequency distribution).

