#### 2 BACKGROUND AND RATIONALE

#### 2.1 MEDICAL BACKGROUND AND SHORT RATIONALE FOR THE CLINICAL TRIAL

Acne vulgaris is a chronic, inflammatory skin disease of the pilosebaceous unit, affecting approximately 80% of young adults and adolescents (Kraining, et al., 1979) (Cunliffe, et al., 1979) (Usatine, et al., 1998) (Leyden, 1995). This is a polymorphic disease in which several types of lesions are usually present at the same time: primary lesions, found in active acne defined by the non-inflammatory and the inflammatory lesions; secondary lesions which came from the first ones and which are defined by scarrings and postinflammatory hyperpigmentation (PIH). It can persist for years and may affect seriously the psychosocial development, resulting in emotional problems, withdrawal from society, and depression (Koo, et al., 1991).

Even if the treatments are efficient in non-inflammatory and inflammatory lesions, secondary acne lesions are not well addressed by the treatments and remain the most unfortunate clinical outcome of acne (Layton, et al., 1994). Acne scars are not uniform and there are several subtypes. Some are more hypertrophic and keloidal in appearance, while others could be more atrophic (Goodman, et al., 2006(a)) (Goodman, et al., 2006(b)). The severity of the acne scars is correlated with the acne grade and also with the delay between the start of the disease and the start of an adapted treatment (Layton, et al., 1994). In her clinical evaluation of acne scarring, Layton indicated that facial scarring occurs to some degree in the majority of acne sufferers (95% of the population) even in the mild to moderate population. Although not universal, acne scars generally occur more with inflammatory acne lesions that were not properly treated (Layton, et al., 1997). Once established, acne scars are believed not to be treatable medically but invasive procedures could offer some improvement (Jacob, et al., 2001) (Jemec, et al., 2004) (Goodman, 2011).

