has been demonstrated that isotretinoin, either oral or topical, protects against UV-induced loss of procollagen, leading to MMP-1, 3 and MMP-9 decrease in relation to the duration of the treatment (Kang, et al., 1997) (Kang, et al., 1998) (Fisher, et al., 2000). This increase in collagen production is clinically appreciated as effacement of wrinkles. After 24 weeks of treatment with topical retinoid, an increase of the epidermal thickness has been observed (Griffiths, et al., 1995) (Kang, et al., 2001) (Philips, et al., 2002). Results generally start to be seen over a few weeks, but as the deposition of new collagen takes place slowly, the skin texture does continue to improve over a 12 month period (Fabbrocini, et al., 2010). Adapalene gel 0.1% and 0.3% formulations have been demonstrated to treat actinic keratoses and solar lentigines and to improve fine and coarse wrinkles, mottled hyperpigmentation, and sallow complexion (Kang, et al., 2003). As photodamage lesions and atrophic acne scars are partially linked to a dermal matrix loss, a potential effect of Adapalene-benzoyl peroxide fixed-dose combination (Adapalene - BPO) to prevent secondary acne lesions (scars) of occurring and/or to improve the pre-existing ones might exist.

Adapalene 0.3% - BPO 2.5% gel is efficacious to treat moderate to severe acne (protocol No.: RD.03.SPR18240) with a trend of numerical superiority compared to Adapalene 0.1% - BPO 2.5% gel in subjects with severe acne.

An exploratory trial (Protocol No.: RD.03.SPR.40183E) has been performed and has shown that over a 24 week period treatment, Adapalene 0.1% - BPO 2.5% reduced the inflammatory and non-inflammatory primary lesions more than the vehicle but also stabilized acne scar counts whereas scars continued to increase with vehicle. Moreover the scar global assessment by the investigator improved with the combination Adapalene - BPO whereas it remained stable with the vehicle. This suggests that the combination Adapalene - BPO both prevents the formation of new acne scars by reducing the number of primary lesions and improves the appearance of pre-existing scars.

It is hypothesized that the treatment effect on acne scars might be stronger with the more concentrated combination Adapalene 0.3% - BPO 2.5% gel.

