#### GALDERMA RESEARCH & DEVELOPMENT Protocol N° RD.03.SPR.105061 Page 26 of 99 CONFIDENTIAL

- 3. Subject with a symmetric number of
  - (a) both inflammatory and non-inflammatory lesions on the whole face, and
  - (b) atrophic acne scars on the whole face
- i.e. there are no more than twice as many lesions of each type on one half of the face than on the other half
- 4. Subject with skin phototype of I to IV on Fitzpatrick's scale (Fitzpatrick, et al., 1993).
- 5. Female of childbearing potential with a negative urine pregnancy test (UPT) at the baseline visit.
- 6. Female subjects of childbearing potential must practice an effective method of contraception during the clinical trial and at least 1 month after the last clinical trial treatment application: medical contraception [combined oral contraceptives (estrogens and progesterone) or implanted or injectable contraceptives] with stable dose for 1 month prior to clinical trial entry, bilateral tubal ligation, hormonal Intra-Uterine Device (IUD) inserted at least 1 month prior to clinical trial entry, strict abstinence (1 month prior to trial entry and agrees to continue for the duration of the trial), condom with spermicide, vasectomized partner (for at least 3 months prior to clinical trial entry).
- 7. Female of non-childbearing potential, eg: post-menopausal (absence of menstrual bleeding for one year prior to clinical trial entry, without any other medical reason), hysterectomy, bilateral oophorectomy.
- 8. Subject having read, understood and signed the approved Informed Consent Form (ICF) prior to any participation in the clinical trial. Subjects under 18 years of age having signed an Assent Form to participate in the clinical trial and their parent(s) or legal representative having read and signed the Informed Consent Form prior to any clinical trial related procedure.
- 9. Subject willing and able to comply with the requirements of the trial protocol, in particular, subject must adhere to the visit schedule, concomitant therapy prohibitions, and must be compliant to the treatment.
- 10. For Canada: Subject informed of the terms pertaining to the Personal Information Protection and Electronic Documents Act (PIPEDA): the subject is willing to share personal information and data and he/she has provided authorization by signing the ICF.
- 11. For France: Subject covered by a National Social Security System.

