### 5.5 CLINICAL TRIAL VISIT DESCRIPTION AND PROCEDURES

# 5.5.1 Visit 1 (baseline) (part I)

- 1. Explain the nature and the constraints of the clinical trial to the subject and to his/her parent(s) or guardian if the subject is under the age of 18.
- 2. If a female subject of childbearing potential agrees to participate to the clinical trial, make sure she is using the requiring method(s) of contraception.
- 3. Ensure the subject (and parent/guardian for subjects under the age of 18) has read, understood, dated and signed the approved Informed Consent Form (ICF).
- 4. Give a dated and signed copy of the ICF to each subject and parent/guardian if applicable.
- 5. Log into the electronic Case Report Form (eCRF) to get a Subject Identification Number (SIN)
- 6. Question the subject about demography (birthdate, race, skin phototype, gender), relevant medical history, prior therapies (stopped within 6 months of the baseline visit and that may have an impact on the inclusion/exclusion criteria) and concomitant therapies.
- 7. Inform subject about authorized and prohibited concomitant therapies.
- 8. Check inclusion/exclusion criteria (see sections 4.2.1 and 4.2.2).
- 9. Conduct a urine pregnancy test (UPT) for female subjects of childbearing potential.
- 10. Count atrophic acne scars of each half-face (see section 7.1.1).
- 11. Perform an Investigator's Scar Global Assessment (SGA) of each half-face (see section 7.1.2).
- 12. Count inflammatory, non-inflammatory acne lesions and nodules of each half-face (see section 7.1.4).
- 13. Perform an Investigator's Global Assessment (IGA) of each half-face (see section 7.1.5).
- 14. Assess the skin roughness score of each half-face (see section 7.1.6).
- 15. Perform the baseline Local Tolerability Assessment (erythema, dryness, scaling, stinging/burning; see Section 7.2.1). Note: Stinging/burning at the baseline visit should be assessed as None (0).
- 16. For selected sites only (and only if subject and parent/guardian accept through the approved ICF, if applicable), take photographs of the face according to the provided procedure.
- 17. For selected sites only, make skin replica for each half-face (if consent given) (see section 7.1.8).
- 18. Provide guidance on the SCARS questionnaire and ask the subject to fill it out for each half-face (see Appendix 1).

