#### **Primary efficacy endpoint:**

• Total atrophic acne scar count per half-face at week 24

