6.3 EFFICACY ANALYSES

6.3.1 Primary efficacy analyses

The primary objective of this study is to demonstrate the superiority of Adapalene 0.3% - BPO 2.5% gel compared to its vehicle, in terms of total atrophic acne scar count at week 24. The mean bilateral difference between products of primary efficacy endpoint will be analyzed by using the Wilcoxon Rank Signed test, testing the hypothesis of equality. The p-value will have to be inferior to 0.05 at week 24, on ITT/LOCF population. Per Protocol analysis will be also performed to assess the robustness of the results obtained on the ITT/LOCF population.

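### The primary test makes no use of the baseline half-face scar counts, so chance baseline imbalance between sides enters the deciding p-value

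*Protocol*

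**What the plan says.** The primary endpoint in Protocol 9.1.1 is "Total atrophic acne scar count per half-face at week 24". Protocol 9.1.4 tests it as follows: "The mean bilateral difference between products of primary efficacy endpoint will be analyzed by using the Wilcoxon Rank Signed test". SAP 6.3.1 repeats the method, "by using the Wilcoxon Rank Signed test, testing the hypothesis of equality", on the ITT/LOCF set with two-sided alpha 0.05. Neither document puts a baseline term in this test.

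Inclusion criterion 3 (Protocol 4.2.1) asks for symmetry of lesions and, under 3(b), of scars, defined as "there are no more than twice as many lesions of each type on one half of the face than on the other half". Visit 1 (Protocol 5.5.1) includes the step "Count atrophic acne scars of each half-face", so the baseline side difference is known for every subject.

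Baseline enters elsewhere in the plan. Percent change in scar count is a secondary endpoint tested with the same method (SAP Table 18), and baseline side differences are tabulated (SAP Tables 13 and 17). None of this alters the primary p-value.

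**The concern.** The week-24 count mixes scars that were there at baseline with scars formed since, while the objective concerns formation. Protocol 2.1 says "Once established, acne scars are believed not to be treatable medically", and reports that in the earlier trial the related product "stabilized acne scar counts whereas scars continued to increase with vehicle". If old scars mostly persist, a subject who starts with more scars on one side tends to end with more on that side, whatever the treatment does. That part of the week-24 difference is noise for the treatment comparison.

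Two things follow. The test has less power than the collected data could give. And if by chance the side assigned to active starts with more or fewer scars on average, part of that imbalance goes straight into the one p-value that decides the trial. The imbalance would be visible in SAP Tables 13 and 17, with no prespecified way to deal with it in the primary analysis.

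**Working it through.** **Inputs from the documents.** Mean side difference 2, SD 4.8, both for the raw week-24 difference (Protocol 9.2.1); two-sided 0.05 (9.1.4); 50 evaluable and 60 enrolled (9.2.2); sides randomised (6.1.2).

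**Assumptions.** The correlation r between baseline and week-24 side differences (D0 and D24), and SD0, the SD of D0, are not in the documents. I use ranges.

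**The plan's own figure.** Normal formula: (4.8 × (1.960 + 0.842) / 2)² = 45.2, so 46. Noncentral t: 48. Divided by the signed-rank efficiency 3/π: 50.3, which matches the stated 50. Simulated signed-rank power is 81% at n = 50, and 87–88% at n = 60 (all ITT, if LOCF does not dilute the effect).

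**Asymmetry allowed.** The widest splits under the 2:1 rule are 6 v 4 at 10 scars, 13 v 7 at 20 and 16 v 8 at 24. An even binomial split cut at 2:1 gives SD0 of 1.6, 3.4 and 4.2 at these totals, so I take SD0 of 2, 3 and 4.

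**Link between r and SD0.** The slope of D24 on D0 is r × 4.8 / SD0. If baseline scars at most persist, the slope is at most about 1, so r is at most SD0 / 4.8 = 0.42, 0.63 and 0.83 at SD0 2, 3 and 4. A value of r = 0.7 needs SD0 of at least 0.7 × 4.8 = 3.36.

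**Power.** Adjustment reduces the SD to 4.8 × √(1 − r²): 4.58, 4.16 and 3.43 at r = 0.3, 0.5 and 0.7. Simulated power of the signed-rank test on D24 − b·D0 (b defined under the fix), n = 50, normal data, raw 81%:

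| r | 0 | 0.15 | 0.3 | 0.5 | 0.7 |
|---|---|---|---|---|---|
| Adjusted | 80% | 81% | 84% | 90% | 97% |

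By SD0 and slope:

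| SD0 | n = 50, slope 0.5 / 1 (raw 81%) | n = 60, slope 0.5 / 1 (raw 87–88%) |
|---|---|---|
| 2 | 82% / 87% | 88% / 92% |
| 3 | 84% / 95% | 90% / 98% |
| 4 | 87% / >99% | 92% / >99% |

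**Type I error of the raw test, n = 60**, split by whether the mean baseline difference reaches 1 standard error (32% of trials):

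| r | 1 SE or more | below 1 SE | overall |
|---|---|---|---|
| 0.3 | 6.4% | 4.3% | 5.0% |
| 0.5 | 9.1% | 3.1% | 5.0% |
| 0.7 | 12.2% | 1.7% | 5.0% |

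After adjustment the rate is 4.6–5.2% in both groups.

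**Imbalance in scars, n = 60.** The 95% limits of the mean baseline difference are ±1.96 × SD0 / √60 = 0.51, 0.76 and 1.01 at SD0 2, 3 and 4. The part reaching the week-24 estimate is the slope times that: 0.25, 0.38 and 0.51 at slope 0.5 (13%, 19% and 25% of the planned effect of 2), and the full amount at slope 1 (25%, 38% and 51%). These are limits, not typical values.

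**Heavy tails** (same SD, excess kurtosis 5, n = 50). Raw 92%. At r = 0, 0.3, 0.5 and 0.7, the adjusted rank test has 91%, 93%, 96% and 99%, and the regression intercept 82%, 86%, 91% and 97%.

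**Integer counts** (assumed: floor of 10 scars, mean total 18.7, 2:1 rule enforced, SD0 3.35, week-24 SD 4.8, n = 50). With 30%, 50%, 70%, 90% and 100% of baseline scars kept, r is 0.21, 0.35, 0.49, 0.63 and 0.70. Raw power is 81–82%; adjusted power is 80%, 84%, 89%, 95% and 98%. Type I error of the adjusted test is 4.8–5.2%.

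**Plain change score.** Its variance is 4.8² + SD0² − 2·r·4.8·SD0. This exceeds 4.8² when r < SD0 / 9.6, that is, when the slope is below 0.5. At SD0 4 and r = 0.3, power at n = 50 falls to 73%, against 81% raw.

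**The case against.** The strongest reply is that nothing here is an error. Randomised sides make the raw test valid, overall type I error is 5%, and the planning SD of 4.8 already contains baseline asymmetry, so 50 subjects give the stated power. All of that stands. The conditional rates of 6–12% apply to a third of trials and are offset in the rest.

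The size of the gain is also not fixed by the documents. Protocol 2.1 suggests that the related product improves the appearance of existing scars. Counting error around the 2 mm threshold would lower the slope. The stable counts in the earlier trial are a group trend and say nothing direct about within-subject correlation. Nor is the cap of 1 on the slope derived: new scars on the side with more active acne could push it higher. This stands too, and is why the results are ranges. The trade is still lopsided: about 1 point of power lost at r = 0, against 9 gained at r = 0.5 and 16 at r = 0.7.

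Criterion 3(b) and the percent-change secondary do help, but they leave the primary p-value as it is.

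On the remedy, b is fitted through the origin and absorbs a little of the effect when baseline is imbalanced. In simulation (n = 60, r = 0.5, true effect 2) the mean adjusted difference was 1.93 at imbalance of 1–2 SE and 1.79 at 2 SE or more. This does not inflate type I error, is already inside the power figures above, and does not affect the regression-intercept estimate.

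**Conclusion.** The concern holds as a matter of efficiency and exposure to chance, not of bias, validity or sample size. The primary test leaves out a baseline value that is collected on every subject and is plausibly prognostic. There is no gain if r is below about 0.15, and little at r of 0.3 or less. The gain is large only if most baseline scars persist and baseline side differences are wide. All sizes rest on assumed r and SD0 and, except where stated, on normal data. The change is worth making because it costs little and the possible loss of power is about 1 point.

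**What to change.** Before unblinding, amend Protocol 9.1.4 and SAP 6.3.1:

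- **Primary test.** Apply the signed-rank test, two-sided at 0.05, to D24 − b·D0, with b = Σ(D0·D24) / Σ(D0²). Swapping a subject's sides flips the sign of both differences and leaves b unchanged, so b can be fixed at the blind data review from right-minus-left data.
- **Supportive.** Keep the raw signed-rank test.
- **Estimate.** Report the intercept of the regression of D24 on D0 with its 95% CI as a prespecified sensitivity estimate. State that this interval and the rank p-value come from different methods and can disagree.
- **Avoid** a plain change score, which can lose power against the raw test.

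If the primary test is kept, add the adjusted analysis to the SAP as the key sensitivity analysis.

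**Cost.** No new data, visits or subjects. Changing the primary test needs SAP wording and a short protocol amendment with IRB/EC approval (Protocol 11.1), and SAP section 7, which declares no change from the protocol, must agree. The sensitivity-only version needs SAP wording alone. One limit remains. The missing-data rule says "If no post-baseline data are available, baseline will be carried forward", so a subject with no post-baseline count has D24 = D0 and contributes (1 − b)·D0. The adjustment shrinks that subject's baseline asymmetry but does not remove it unless b is 1.

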#### 9.1.5 Interim analysis

Interim analysis will be performed when all subjects will have completed the week 24 visit (Part I). For this interim analysis, all available variables will be analyzed. This interim analysis is dedicated to provide the statistical results and is not meant to condition to any premature study termination. As all statistical analyses were planned during part I, this interim analysis will have no impact on the type I error, and the efficacy results will be considered as final.

